## 5. STUDY DESIGN & METHOD

#### STUDY DESIGN

90 patients aged 20-60 years who were diagnosed with partial supraspinatus tear and met the inclusion criteria of the study will be included in the study. Patients will be randomized into three groups: 30 patients in the first group who have 5 sessions of high-intensity laser, 30 patients in the second group who have 10 sessions of high-intensity laser, and 30 patients in the third group control group who have only exercises. It was planned to give 5 sessions of laser+exercise every other day to the the first group, 10 sessions of laser+exercise every other day to the second group, and only exercise program three days in a week to the control group. All groups will be evaluated with joint range of motion (ROM) (measurements including abduction, adduction, flexion, extension, internal and external rotation by goniometer according to neutral 0 position), visual analog scale (VAS), shoulder pain dissability index, quickdash, constant score at 0th month, 1st month, 3rd and 6th months.

#### **DETAILS of METHOD**

Patients in the laser group will be given hiltherapy (high-intensity laser) with the HIRO 3 device every other day. One session of laser therapy application consists of 3 phases: the beginning, the middle and the ending phase. The initial phases are fast scanning and the ending phase is slow scanning. A total of 2000 J will be applied to the rotatorcuff muscles, the upper part of the trapezius muscle, the deltoid muscle and the pectoralis major muscle, 1000 J in the rapid scan phase and 1000 J in the finishing phase. In the middle phase, 50 J will be applied for the trigger point (hard intramuscular points that cause referred pain) in each muscle and a maximum of 500 J in total. The total dose prescribed for patients in one session will be 2500 J. Each phase will be 15 minutes on average and the session will last for 45 minutes in total. The laser probe will be applied with 90 degrees. During the application, the practitioner and the patient will have protective glasses.

Patients in the laser group will be given hiltherapy (high-intensity laser) with the HIRO 3 device every other day. One session of laser therapy application consists of 3 phases: the beginning, the middle and the ending phase. The initial phases are fast scanning and the ending phase is slow scanning. A total of 2000 J will be applied to the rotatorcuff muscles, the upper part of the trapezius muscle, the deltoid muscle and the pectoralis major muscle, 1000 J in the rapid scan phase and 1000 J in the finishing phase. In the middle phase, 50 J will be applied for the trigger point (hard intramuscular points that cause referred pain) in each muscle and a maximum of 500 J in total. The total dose prescribed for patients in one session will be 2500 J. Each phase will be 15 minutes on average and the session will last for 45 minutes in total. The laser probe will be applied with 90 degrees. During the application, the practitioner and the patient will have protective glasses.

30 patients will be included to control group. They will take only exercise program three times in a week. **Description of Transactions on Working Days & Visits** 

Patients diagnosed with partial supraspinatus tear on working days will be evaluated in the ftr outpatient clinic and suitable patients will be included in the study. Demographic information of the patients will be recorded. Consent will be obtained from the patients on the same day. Patients randomized to 3 groups will be included in the treatment protocol prescribed for each group at 0, 1, 3 and 6 month will be evaluated with VAS, shoulder

# Protocol name/ version number /date: Efficacy of high-intensity laser therapy in patients with partial supraspinatus tears Versivon no: 02 - Tarih: 02.12.2020

pain dissability index, quickdash, constant score and range of motion including abduction, adduction, flexion, extension, internal and external rotation by goniometer according to the neutral position.

#### Randomization

After the subjects included in the study are informed about the study, they will be randomized into 3 groups according to their order of application.

Blindness

None

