#### 4. SELECTION OF POPULATION & PATIENTS TO BE RESEARCHED

Disease	Partial supraspinatus tear
Number of Patients & Characteristics	women Man Age 20-65 Healthy : Patient :90 Total : 90

Volunteers will be included in the study among the patients who applied to the FTR outpatient clinic and were diagnosed with a partial supraspinatus tear of the shoulder.

Inclusion Criteria:

\*age between 20-65 years

\*Patients with VAS>4 pain in the shoulder for at least 3 months

\*Patients with at least 25% loss in the range of motion of the joint compared to the contralateral side, especially in abduction and external rotation, or on physical examination or positivity of at least one of the impingement tests including jobb, lift off, ERLS, speed, yergeson, O Brien's test, dropparm tests or popeye signs. \*Diagnose of partial supraspinatus with ultrasound or MR -

Exclusion Criteria:

\* Patients with incomplete skin integrity, hyperemia, signs of infection or tattoos

\*Patients with suspected full-thickness tear

\*History of rheumatic disease (rheumatoidarthritis, osteoarthritis, PMR)

\*Patients with accompanying shoulder pathology such as calcifictendinitis

\*History of malignancy

\*Surgery, manipulation, mobilization, arthroscopy performed on the affected shoulder

\*Steroid, local anesthetic, hyaluronic acid injection, cnesiotaping or neural therapy in the affected shoulder in the last 3 months

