#### Statistical & Analytical Methods

The data will be analyzed with the SPSS 18.0 package program. GraphPad for Windows will be used in the randomization process. Continuous variables will be presented as mean and standard deviation or median (25p-75p). Categorical variables will be presented as percentages. The conformity of the data to the normal distribution will be evaluated with the Shapiro Wilk test. Analysis of variance (ANOVA) and split-mixed ANOVA will be used in the analysis of within-group changes and in repeated measures of significance between the differences between groups. Tukey and Games Howell tests will be used in post-hoc tests.

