**Ensuring Confidentiality** 

The investigator will ensure that the names of the patients are kept confidential and that the identities of the individuals are protected from unauthorized parties, that the patients will be identified only by the initials of the name-surname and randomization number on the Case Report Form; It will be explained that any document that identifies the patient will be kept in complete confidentiality by the principal investigator, and that the investigator may authorize appropriate legal authority(s) to review patients' files in line with Good Clinical Practices and legal requirements.

Protocol Changes and Approval of Changes

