# Protocol name/ version number /date: Efficacy of high-intensity laser therapy in patients with partial supraspinatus tears Versiyon no: 02 - Tarih: 02.12.2020

All protocol adjustments will not be made without the approval of the local ethics committee for any regulation that may affect the safety of patients or the conduct of the study, prior to the implementation of any changes to the protocol.

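### Allocation follows order of application in an open trial and no concealment is described, so staff who judge eligibility could know the next arm

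*Combined protocol and SAP*

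**What the plan says.** All text on allocation is in the combined protocol and SAP:

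- **Section 5, Randomization.** Once informed about the study, "they will be randomized into 3 groups according to their order of application". The Blindness entry that follows reads None.
- **Section 10, Statistical & Analytical Methods.** "GraphPad for Windows will be used in the randomization process". No sequence type, block size or list holder is given.
- **Section 11, Ensuring Confidentiality.** Patients are "identified only by the initials of the name-surname and randomization number on the Case Report Form".
- **Section 5, Description of Transactions on Working Days & Visits.** Patients "will be evaluated in the ftr outpatient clinic and suitable patients will be included in the study". On timing: "Consent will be obtained from the patients on the same day".
- **Section 4, exclusion criteria.** One criterion is "Patients with suspected full-thickness tear".
- **Section 6, Data Recording.** A case report form is also kept for patients who do not complete the study, including at screening before randomisation if a form had been started.

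The target is 30 patients in each of three arms. No section describes envelopes, central or third-party allocation, or any separation between the person who enrols and the person who assigns.

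**The concern.** The planned ANOVA comparisons treat the three arms as differing only by chance at entry. That holds if the person deciding whether a patient is suitable cannot know which arm comes next. The protocol supplies no such protection, and two features make the gap matter more here. Treatment is open, so past assignments are visible. Eligibility also leaves some room for judgement, both in who is suitable and in whether a full-thickness tear is suspected.

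If the next arm is known, a patient expected to do well or badly can be included, deferred or turned away accordingly. A difference in month-0 scores would at least be visible, and if it is stable over time it largely cancels in the group-by-time test. A difference in expected recovery that month-0 scores do not capture would not cancel. It would look like a laser effect, and no analysis could reliably remove it afterwards. The primary purpose, showing efficacy of laser, rests on this comparison.

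**Working it through.** **1. The sample size is not at issue.** Section 10 states f = 0.40, 90% power, 5% type 1 error and 84 patients, raised to 90. For a one-way ANOVA with three groups and noncentrality λ = N·f², power is 0.895 at N = 81, 0.907 at N = 84 and 0.926 at N = 90. The smallest N reaching 0.90 is 83, which is 84 with equal arms. The stated figure reproduces, and the allocation point does not change it.

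**2. Two readings of the rule.**

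| Reading | Support in the text | Is the next arm hidden? |
|---|---|---|
| Arms assigned in rotation by arrival | Literal wording of the Randomization section | No |
| Arriving patients take the next entry on a random list | The verb used there, GraphPad in Section 10, the randomization number in Section 11 | Not stated |

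GraphPad bears on how a sequence is generated. A number on the case report form identifies the patient. Neither hides the next assignment. Randomisation does come after inclusion, but that order protects only if the arm is unknown at the moment of inclusion.

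**3. How predictable the next arm could be.** The documents do not say which scheme applies, so these are cases, not estimates. The best guess is the arm with most places left.

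- Rotation, or a list in open view: 100%.
- Blocks of 3, size known and past assignments seen: (1/3 + 1/2 + 1)/3 = 0.611.
- Blocks of 6, same conditions, exact recursion: 0.561.
- A single list fixed at 30 per arm, past assignments known, exact recursion: 0.409.
- Concealed unrestricted list: 1/3, about 33%.

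**4. What steering could do to the tests (illustration).** Assumptions: no laser effect; the control arm is shifted by d SD and the two laser arms are equal; 30 per arm; α = 0.05. The shifts and correlations are assumed, because the documents give none.

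*One-way ANOVA on a post-treatment score.* With arm means (0, 0, d), the SD of the means is d·√2/3, so f = d·√2/3 and λ = 90·(2d²/9) = 20d², on 2 and 87 df.

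| d | λ | False-positive rate |
|---|---|---|
| 0.1 | 0.2 | 0.065 |
| 0.2 | 0.8 | 0.113 |
| 0.3 | 1.8 | 0.201 |
| 0.5 | 5.0 | 0.489 |

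*Group-by-time test, four visits, equal correlation ρ between visits, shift at months 1, 3 and 6 only.* The centred arm effects have sum of squares (2/3)d². The centred visit pattern (−3/4, 1/4, 1/4, 1/4) has sum of squares 3/4. Hence λ = 30·(2/3)·(3/4)·d²/(1−ρ) = 15d²/(1−ρ), on 6 and 261 df.

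| d | ρ = 0.3 | ρ = 0.5 | ρ = 0.7 |
|---|---|---|---|
| 0.1 | 0.058 | 0.062 | 0.070 |
| 0.2 | 0.086 | 0.102 | 0.144 |
| 0.3 | 0.140 | 0.183 | 0.296 |
| 0.5 | 0.352 | 0.489 | 0.747 |

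A simulation of the mixed ANOVA (20,000 runs per cell) agrees with these within 0.005.

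*Group-by-time test, stable shift at all four visits.* The centred visit pattern is zero, so λ = 0 and the rate stays at 5%. The simulation gave 0.049, 0.049 and 0.053 for shifts of 0.2, 0.3 and 0.5 SD at ρ = 0.5.

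**The case against.** The fair counter-case is that this is a short protocol with an awkward sentence. It repeatedly says patients are randomised, names software for it, and refers to a randomization number. The more coherent reading is then that consecutive patients take the next entry on a generated list. Open treatment does not prevent concealment. Eligibility has firm limits too: a pain threshold lasting at least 3 months, imaging diagnosis, and a set loss of motion or a positive test. The screening forms in Section 6 leave a partial record of who was assessed.

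Much of this is right as far as it goes. Non-random allocation is not proven, and the firm criteria narrow the room for steering. But the list reading does not close the gap, because a list that recruiters can see exposes the next arm just as rotation does. The remaining criteria still call for judgement, and a screening form is not concealment.

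The objection to the figures also has force. Nothing converts a guess rate into a shift in SD, and the larger false-positive rates follow only from the larger assumed shifts. They further require staff to foresee recovery that month-0 scores do not show. The block figures of 61% and 56% could arise even with sealed envelopes if the block size were known, so they are a reason for varying, undisclosed blocks, not a measure of missing concealment. An unrestricted list would not guarantee 30 per arm; a single list fixed at 30 per arm gives about 41%. The calculations show how the tests would respond to steering, and the conclusion does not depend on any of them.

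**Conclusion.** The concern holds. The stated rule is either predictable by construction or silent on whether the next arm is hidden, and no other section supplies the safeguard. Selection bias is therefore possible and cannot be excluded, in an open trial whose main inference depends on comparable arms. It is not demonstrated.

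Its size cannot be estimated from the documents. Under the assumed shifts in prognosis of 0.1 to 0.5 SD, the group-by-time false-positive rate runs from about 6% to 49% at a correlation of 0.5. Across correlations of 0.3 to 0.7, a 0.5 SD shift gives about 35% to 75%. A stable entry difference leaves the rate at about 5%. The point must be fixed because staff cannot apply the current sentence unambiguously, and the harm could not be undone in the analysis.

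**What to change.** In Section 5, Randomization, remove the clause about order of application and state:

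- 1:1:1 allocation from a random list generated in GraphPad, for example in permuted blocks of varying, undisclosed size;
- the list is prepared and held by a team member who takes no part in enrolment;
- assignments are kept in sequentially numbered, opaque, sealed envelopes;
- each envelope is opened only after eligibility, consent and month-0 measurements have been recorded.

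Make Section 10 refer to the same list. Numbered envelopes still follow the order of entry, so nothing useful is lost by removing the clause. Another mechanism that hides the next assignment equally well would also serve.

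The cost is a paragraph of wording, a set of envelopes and a list holder. The documents do not show whether a non-enrolling team member is already available, so this should be confirmed. The change also needs ethics approval, since Section 11 says that "All protocol adjustments will not be made without the approval of the local ethics committee". No extra patients, visits or procedures are needed, and the sample size is unaffected.

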#### **Ensuring Patient Compliance**

Detailed information about the purpose of the study and its scientific contribution will be given to the patients and their relatives. Patients and their relatives will be informed that their names will be kept confidential. Parts that cannot be understood in the informed consent form will be explained in more detail. They will be informed that the study has the right to withdraw from the study at any time.

#### Materials to be Used & Storage Conditions & Responsibilities

Thera band will be used for the exercises.

6. COLLECTION OF STUDY DATA

#### Data Recording/ Case Report Forms

A Case Report Form will be completed for each registered patient and signed by the responsible investigator or an authorized representative of the study staff. This also applies to enrollments for patients who did not complete the study (even during pre-randomisation screening, if a case report form was prepared). If a patient withdraws from the study, the reason for this will be recorded on the Case report form. If a patient is withdrawn from the study due to a treatment-limiting adverse event, every effort will be made to clearly document the outcome. All forms must be typewritten or filled with indelible ink and be legible. Errors can be crossed out, but errors cannot be erased; correction is entered and the change is initialed and dated by the researcher or his authorized representative. The investigator will ensure that the data reported to the sponsor in case report forms and all required reports are correct, complete, legible and processed in a timely manner. The researcher is responsible for the accuracy of the data transferred on the forms and will sign these forms to show their compatibility with the recorded data.

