**Exclusion Criteria and Practices in this Case** 

Patients will be excluded from the study if they do not attend follow-up and laser sessions regularly.

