## **10. STATISTICAL PROCEDURES**

Sample Size

Sample size calculation was made using G\*POWER 3.1.9 program. Using the findings of a similar study conducted before (6), it was predicted that a high level of effect size would be obtained between the groups (f=0.40) for the SPADI score of  $22\pm1.2$  for the 6th month before and after the treatment and  $41.4\pm2.6$  for the control group (f=0.40), 90% power, and type 1 error level: 5%, it is aimed to reach at least 84 people in total, and at least 90 people considering that there may be losses in the follow-up.

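### No provision to keep assessing patients who stop laser, and split-mixed ANOVA drops anyone with an incomplete set of visits: two separate losses, needing two separate fixes

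*Combined protocol and SAP*

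**What the plan says.** Three parts of the protocol decide what happens to a patient who does not finish as planned.

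- **Section 6, Data Recording/ Case Report Forms.** On treatment-limiting events: "If a patient is withdrawn from the study due to a treatment-limiting adverse event, every effort will be made to clearly document the outcome". On withdrawal generally: "If a patient withdraws from the study, the reason for this will be recorded on the Case report form". On the duty to complete a form: "This also applies to enrollments for patients who did not complete the study". So values up to the point of leaving will exist, but no month 1, 3 or 6 assessment is required afterwards.
- **Section 4, Exclusion Criteria and Practices in this Case.** "Patients will be excluded from the study if they do not attend follow-up and laser sessions regularly".
- **Section 10, Statistical & Analytical Methods.** "Analysis of variance (ANOVA) and split-mixed ANOVA will be used in the analysis of within-group changes", and also for differences between groups over the repeated measurements. The software is SPSS 18.0. No analysis population, missing-data rule or sensitivity analysis is given.

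Section 5 sets four assessments: "constant score at 0th month, 1st month, 3rd and 6th months". It gives laser every other day to two arms (5 or 10 sessions) and exercise only to the third. Section 8 foresees skin reactions and burns during treatment. The sample size paragraph answers attrition only with a number: "at least 90 people considering that there may be losses in the follow-up".

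**The concern.** Stopping a treatment and leaving a study are different things. A patient who stops laser can still attend at months 1, 3 and 6, and those values are needed to compare the groups as randomised. The plan never describes that status.

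The control arm has no laser, so laser-related stops cannot occur there, and the 10-session arm has twice the exposures of the 5-session arm. If those who stop fare worse, their absence flatters laser against control (the primary purpose) and may flatter 10 sessions against 5 (the secondary purpose).

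The second loss is unrelated to adverse events. A classical split-mixed ANOVA across four visits needs all four values from each patient. Someone in any arm who leaves after month 1 or 3, or misses one visit, contributes nothing to that analysis, although the case report form holds the other values. What remains is a completer analysis, which is biased when patients doing badly are the ones who leave.

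**Working it through.** **The plan's own figure.** Three groups, f = 0.40, alpha 0.05, one-way ANOVA F test with noncentrality N × f². Power is 0.903 at N = 83 and 0.907 at N = 84, so 84 is the smallest balanced total with 90% power. It reproduces. The allowance for losses is 90 − 84 = 6, and 6/90 = 6.7%.

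**Is power the issue?** No. With the two laser arms equal and f = 0.40, losing 0, 3, 6 or 10 patients from each laser arm gives power 0.926, 0.916, 0.903 or 0.878. The issue is bias.

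**Timing of laser-related stops.** Assume laser starts at about month 0. With a session every other day, session 5 falls on day 1 + 4 × 2 = 9 and session 10 on day 1 + 9 × 2 = 19. Both courses end before the month 1 visit, so a patient withdrawn during laser normally has a baseline value only.

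**Loss 1: size.** If k of 30 patients are removed and they would have scored g SPADI points worse than the rest, the mean of those left is too low (too good) by (k/30) × g. The documents give no stop rate and no g, so both are assumed.

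- k = 2, g = 10: 2/30 × 10 = 0.7 points
- k = 3, g = 15: 3/30 × 15 = 1.5 points
- k = 5, g = 20: 5/30 × 20 = 3.3 points

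The SPADI means in the sample size paragraph differ by 41.4 − 22 = 19.4 points, so this is 0.7/19.4 = 4% to 3.3/19.4 = 17% of that difference.

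**Loss 1: can analysis recover it?** A simulation of these three cases (SD 20, between-visit correlation 0.6, stops unrelated to baseline) gave month 6 bias of −0.76, −1.47 and −3.33 for completers. After regression on baseline it was −0.76, −1.47 and −3.32. Baseline adjustment recovers essentially nothing; only the later assessments would help.

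**Loss 1: false positives.** With no true difference and removal only in the laser arms (5,000 runs, those removed 0.5 to 1.0 SD worse), the one-way ANOVA rejected in 0.045 to 0.051 of runs at 5% removal, 0.049 to 0.062 at 10% and 0.061 to 0.099 at 20%.

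**Loss 2: size.** Assume SD 20, correlation 0.6, and 2 to 4 of 30 leaving after month 1, mainly those with worse month 1 scores (4,000 runs). Month 6 completer bias was −0.9 to −1.5 with mild selection and −1.1 to −2.2 with stronger selection. Using months 0 and 1 of those who left reduced it to about 0.1 or less. In this case the observed visits do carry the information, and the ANOVA discards it.

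**The case against.** Several points on the other side stand.

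- The section 6 sentence is conditional and concerns record-keeping. A reader might infer a rule that every patient who stops laser must leave the study; the text does not say so. It also leaves "the outcome" undefined: most naturally the outcome of the event, but that is a reading. What holds is that no off-laser, still-assessed status appears anywhere.
- A reader might join the two losses and infer that the ANOVA makes poor tolerators of laser disappear. The timing does not support that: such a patient usually has only a baseline value to discard, and a better model would not restore the rest.
- Changing section 6 alone might achieve nothing, because the attendance exclusion in section 4 could still remove a patient who has stopped laser.
- Listwise deletion follows from the named method and is not written in the plan. Plain ANOVA is also named; run visit by visit, it would keep earlier values, though not supply those after withdrawal.
- It is tempting to compound a per-visit loss, for example 1 − (1 − 0.05)³ = 14.3%, and set it against the 6.7% allowance. If 5% is dropout, any month 6 analysis shares that loss; if it is sporadic missed visits, it has nothing to do with adverse events. It does not measure this problem.
- In the loss 2 simulation departures depend on observed scores, so recovery by a method using those scores is built in. Weaker selection gives smaller bias, from about 0.65 points.
- Allocation is not blinded. Disappointed control patients could also leave and push the comparison the other way, so the net direction is not certain.

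None of this supplies continued assessment after stopping laser or a repeated-measures method that uses partial records.

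**Conclusion.** The point holds as two distinct losses.

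1. Patients who stop laser have no route to continued assessment under sections 4 and 6. On the assumed stop rates and gaps, a laser arm's mean SPADI looks 0.7 to 3.3 points too good. No analysis method repairs this, because normally only baseline exists.
2. Split-mixed ANOVA drops incomplete records from any arm. Under assumed selection on month 1 score, month 6 bias is about 1 to 2 points, mostly avoidable with data already collected.

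The stop rate, gap, SD, correlation and selection strength are all assumptions. If stops and dropouts are rare, both biases are small, and power is little affected either way. The change is worth making because it is cheap and, for loss 1, cannot be made after the data are in. Confidence is medium.

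**What to change.** **Sections 6 and 4, together.** For data collection, separate stopping laser from leaving the study. Patients who stop laser, for an adverse event or otherwise, are asked to keep the scheduled month 1, 3 and 6 assessments unless they withdraw consent, and are analysed in their allocated group. Reword the attendance exclusion so that it does not remove them. This says nothing about when laser should be stopped, which is a clinical matter.

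**Section 10.** Replace split-mixed ANOVA with a linear mixed model for repeated measures (group, visit, group × visit; the MIXED procedure in SPSS), including every randomised patient with any observed visit.

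**Cost.** About one sentence in each of sections 6 and 10, and a matching edit in section 4. No visits are added to the schedule; a few patients off laser attend assessments they would otherwise have missed. The model assumes data are missing at random, which continued assessment makes less critical. The estimated effect may be slightly smaller.
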